8.1.2. Display of TEAE

Analysis set: Full Analysis Set

Analysis items: TEAE

Category Classification:

Causal relationship with study drug [related, unrelated]

Severity [Mild, Moderate, Severe]

Date of onset [1<= - <29, 29<= - <58, 58<= - <=Max]

Analysis Methods: For the above analysis items, the following analysis will be performed. The data will be coded using the MedDRA dictionary and be summarized into SOC and PT. SOC's will be sorted in alphabetical order, then PTs will be sorted in decreasing frequency order.

- 1) All TEAEs (by SOC/PT)
- 2) TEAEs related to study drug (by SOC/PT)
- 3) TEAEs by severity (by SOC/PT)
- 4) TEAEs related to study drug by severity (by SOC/PT)
- 5) TEAEs leading to study drug discontinuation (by SOC/PT)
- 6) Serious TEAEs (by SOC/PT)
- 7) Non-serious TEAEs (by SOC/PT)
- 8) Serious TEAEs related to study Drug (by SOC/PT)
- 9) Serious TEAEs leading to study drug discontinuation (by SOC/PT)
- 10) TEAEs leading to death (by SOC/PT)
- 11) TEAEs by date of onset (by SOC/PT)

The number of subjects and incidence rates will be calculated in the same manner as mentioned in 8.1.1.

8.2. Other Evaluation

8.2.1. Evaluation of Weight

Analysis set: Full Analysis Set

Analysis items: Weight

Time Point: Baseline, Week 4, Week 8, End of the treatment period

Analysis Methods: For the above analysis items, the following analysis will be performed

- (1) Summary statistics for observed values and post-treatment changes (post-treatment value – baseline value) will be calculated at each time point.
- (2) For observed value, case plots will be illustrated at each time point.

9. LISTING

Listing of the following data will be presented.

- Demographic Data
- Medication History
- Medical History, Concurrent Medical Conditions
- Insomnia History
- Depression History
- Weight, BMI
- HAM-D17
- 3DSS
- Actigraphy
- Eligibility
- Study Drug Compliance
- Status at the end of Study
- PGI
- Sleep Diary
- Adverse Event
- Concomitant Medications
- Overdose

10. CONSIDERATIONS on STATISTICAL ANALYSIS

10.1. Adjustments for Covariates

Adjustments for covariates will not be performed.

10.2. Handling of Dropouts or Missing Data

Any imputation for missing data will not be performed.

10.3. Criteria for Interim Analysis and Early Discontinuation

No interim analyses will be performed.

10.4. Multicenter Studies

No statistical adjustments will be made to compensate for multi-center study.

10.5. Multiple Comparisons/Multiplicity

No statistical adjustments will be made for multiple comparisons.

10.6. Examination of Subgroups

The subgroup analyses will be performed to examine the primary endpoints using the same analysis methods as 7.1.1(1). The analyses will be performed for the data at the end of treatment period only.

Subgroups:

- Medication history
[Previous use of Benzodiazepine hypnotics,
No previous use of Benzodiazepine hypnotics (Previous use of Non-benzodiazepine hypnotics),
No previous use of Benzodiazepine hypnotics (No previous use of Non-benzodiazepine hypnotics and previous use of other hypnotics),
No previous use of hypnotics]
- Concomitant use of Benzodiazepine anxiolytics [Yes, No]
- Concomitant use of SSRI or SNRI [Yes, No]
- Duration of insomnia [< 3years, 3years<=]
- Duration of depression [< 3years, 3years<=]
- Phase scale score in 3DSS at Baseline [< 9, 9<=]

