13.1.5 Significance level and confidence coefficient

Significance level: 5% (two-sided testing)

Confidence coefficient: 95% (two-sided estimation)

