13.3 Determination of Sample Size

The sample size is set to 30 in light of feasibility of this study to investigate the effect of ramelteon in insomnia patients with depression. This planned sample size is not based on statistical power calculation.

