7. EFFICACY EVALUATIONS

7.1. Primary Endpoint and the Analytical Methods

7.1.1. Change from Baseline in Sleep Latency by Actigraphy

Analysis set: Full Analysis Set

Analysis items: Sleep latency by actigraphy

Time point: Baseline, Week 4, Week 8, End of the treatment period

Analysis methods: For the above analysis items, the following analysis will be performed.

- (1) As the analyses for primary endpoint, summary statistics and two-sided 95% confidence interval (CI) of the mean will be calculated for both change and percentage change from baseline to the end of treatment period, and one sample t-test will be conducted to assess the change within a subject. The same analyses as described above will be performed for change and percentage change at Week 4 and Week 8. In addition, mean plots with +/- SD for change and percentage change will be displayed at each time point.
- (2) For change and percentage change from baseline to each time point, case plots will be illustrated at each time point.
- (3) For observed value at each time point, case plots will be displayed, and summary statistics and two-sided 95% CI of the mean will be calculated. Mean plots with +/- SD will be also displayed at each time point.

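### SAP 10.6 gives only within-level subgroup results and never compares levels, so differing significance can easily be misread as a differing effect

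*SAP*

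**What the plan says.** SAP 10.6 names six subgroup variables: previous hypnotic use (four levels), and benzodiazepine anxiolytic use, SSRI/SNRI use, duration of insomnia, duration of depression and baseline 3DSS phase score (two levels each). The method is given by reference: "The subgroup analyses will be performed to examine the primary endpoints using the same analysis methods as 7.1.1(1"). The time point is restricted: "The analyses will be performed for the data at the end of treatment period only".

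SAP 7.1.1(1) says that "summary statistics and two-sided 95% confidence interval (CI) of the mean will be calculated for both change and percentage change from baseline", with the final on-treatment assessment as the comparison point. On testing, it adds that "one sample t-test will be conducted to assess the change within a subject". It also provides mean plots.

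Three other statements bear on the point. SAP 10.1: "Adjustments for covariates will not be performed". SAP 10.5 rules out any multiplicity adjustment. Protocol 13.1.5: "Significance level: 5% (two-sided testing"). On size, Protocol 13.3 says "The sample size is set to 30 in light of feasibility of this study" and "This planned sample size is not based on statistical power calculation".

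Neither document specifies a difference between subgroup levels, an interval for such a difference, an interaction term, or a rule for reading the subgroup results. The SAP revision history shows that section 10.6 was added in version 2.0 (26 FEB 2018).

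**The concern.** A subgroup analysis is of interest because the change in sleep latency might differ between kinds of patient. Testing each level against zero does not address that. The p-value in a level depends on the number of patients in it as well as on the change, so two levels with the same true change will often fall on opposite sides of 5%, and more readily when their sizes are unequal.

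The planned output covers 4 + 5 × 2 = 14 levels. Change and percentage change are both tested, which makes 28 p-values. None of them compares two levels. A reader given that table has only the pattern of significance from which to judge whether levels differ, and that pattern is a poor guide. The risk is a report suggesting that one kind of patient responds and another does not, with no analysis behind the statement.

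**Working it through.** The plan has no figure to reproduce: the sample size is a feasibility number and no power is stated. The check asks how often the planned output would show one level significant and the other not when the true change is the same in both.

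**Inputs from the documents.** N = 30 in a single arm (Protocol 13.3); one-sample t-test (SAP 7.1.1(1)); 5% two-sided (Protocol 13.1.5).

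**Assumptions, not in the documents.** All 30 patients evaluable; a common standardised mean change d (mean change divided by SD of change) from 0.3 to 1.0; illustrative splits of 15/15, 20/10 and 24/6. The value d = 0.53 is included because it gives the test in all 30 patients about 80% power.

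**Formulas.** Power in a level of size n is P(|T| > t(0.975, n−1)), where T is non-central t with n−1 degrees of freedom and non-centrality d√n. At d = 0 this returns 0.05, as it should. With powers p and q in the two levels, the chance that exactly one is significant is p(1−q) + q(1−p).

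**Example.** At d = 0.5 and 20/10, p = 0.565 and q = 0.293. Then 0.565 × 0.707 + 0.293 × 0.435 = 0.399 + 0.127 = 0.527 (from unrounded powers), or 53%. All 30 patients together would have 75% power.

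**Chance that exactly one of two levels is significant, same true change in both**

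| d | 15/15 | 20/10 | 24/6 |
|---|---|---|---|
| 0.3 | 31% | 32% | 33% |
| 0.4 | 42% | 44% | 48% |
| 0.5 | 49% | 53% | 60% |
| 0.53 | 50% | 54% | 63% |
| 0.6 | 49% | 55% | 67% |
| 0.8 | 29% | 40% | 63% |
| 1.0 | 10% | 20% | 49% |

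**Direct comparison.** A pooled two-sample t-test of change between levels has a 5% false-signal rate by construction (simulated: 4.5% to 5.8%).

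**Over the five two-level variables.** In simulation with independent random splits, at least one variable showed discordant significance in 82% to 88% of trials at d = 0.5, and in 24% to 91% at d = 1.0. For direct comparisons the figure is about 1 − 0.95⁵ = 22.6%.

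**Precision of the direct comparison.** The unadjusted 95% half-width, in SDs of change, is t(0.975, 28) × √(1/a + 1/b), with t = 2.048:
- 15/15: 2.048 × √(2/15) = 0.75
- 20/10: 2.048 × √(1/20 + 1/10) = 0.79

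At 15/15, a true difference of about 1.06 SD would be needed for 80% power.

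**Medication history.** Four levels average 30/4 = 7.5 patients. At d = 0.53 the power in a level of 7 or 8 is 22% or 25%.

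**The case against.** The strongest reply is that the study is exploratory, sized for feasibility, and that the subgroups are supplementary and confined to one time point. The primary result does not depend on them, and the half-widths above show that the missing contrast would seldom be informative. All of this is true, and it limits the consequence. It excuses imprecision, but not leaving out the comparison. A wide interval for the difference tells the reader how little is known; a pair of p-values hides it.

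The size of the problem also rests on assumptions. Discordance peaks at middling effects and falls when the effect is large and the split even (10% at d = 1.0 and 15/15). The 67% maximum needs a 24/6 split. That stands, and is why a range is given.

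Four stronger readings are tempting but not supported:

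- **That the SAP will declare effect modification from differing p-values.** It says only that the primary endpoint will be examined in subgroups. The misreading is a risk the output creates, not a stated rule.
- **That t-tests are the only output.** Summary statistics and a 95% interval are produced for each level. These are useful, but they too are within-level.
- **That levels with higher baseline latency must regress further.** A level with a truly higher mean regresses towards its own mean, and the run-in latency floor in inclusion criterion 9 may truncate such a level less. The direction is not established.
- **That the subgroups were chosen after seeing results.** The revision history shows a late addition. It does not show that data had been examined.

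Finally, the design is uncontrolled (Protocol 6.2), so even a clear difference in change between levels could reflect natural course or regression to the mean. The comparison must not be presented as a test of differing drug effect.

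**Conclusion.** The point holds as a shortcoming of the subgroup method. SAP 10.6 provides only within-level results, and nothing in either document compares levels. Under a common true change, discordant significance in a two-level variable occurs in roughly 10% to 67% of cases over d = 0.3 to 1.0 and splits of 15/15 to 24/6, against 5% for a direct comparison. These figures assume 30 evaluable patients and normally distributed change; the effect sizes and splits are illustrative. The multi-variable figures also assume independent splits.

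The change is worth making because it is cheap and replaces a misleading display with the relevant quantity. It is not a flaw in the primary analysis, and it would not enable the study to detect modest subgroup differences.

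**What to change.** Amend SAP 10.6 as follows.

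1. For each level, report n, mean change and its 95% confidence interval, without a within-level p-value.
2. For each two-level variable, add the between-level difference in mean change with its 95% confidence interval, unadjusted. A version adjusted for baseline sleep latency can be an optional sensitivity analysis. It would need an exception to SAP 10.1, and it should be read with care because levels that truly differ at baseline are not made comparable by adjustment.
3. Keep the four medication-history levels as descriptive output. A collapsed contrast, such as any previous hypnotic use against none, is optional.
4. State that differences between levels are read only from the contrast and not by comparing p-values; that the contrasts are exploratory and imprecise (unadjusted half-width about 0.75 SD at 15/15 and 0.79 SD at 20/10); that without a control arm they describe differences in change and not in drug effect; and that the subgroups were added in SAP version 2.0.

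The cost is a paragraph of SAP text and a few simple contrasts on data already collected. The price in reporting is wide intervals and fewer p-values.

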11. REVISION HISTORY

Ver.	Date	Author	Revised Content	Reason for Revision
1.0	3 JUN 2016	PPD	-	
2.0	26 FEB 2018	PPD	
5.OTHER DATA HANDLING
 
Add the endpoints below:
 
[Actigraphy]
 
 • Daily variation of sleep latency 
[Sleep Diary]
 
 • Daily variation of sleep latency 
[HAM-D17]
 
 • HAM-D17 total score (excluding sleep related score) • HAM-D17 total score (sleep related score only) 
[Demographic Characteristics]
 
 • Disease Duration (year) 
[Non-serious TEAE]
	To add the endpoints.
			
6.1.3. Subject Disposition
 
Modify the title below:
 
(Before) 6.1.3.1. Status at the End of Treatment Period
 
(After) 6.1.3.1. Status at the End of Study
 
Modify the endpoint below:
 
(Before) Status at the end of treatment
 
(After) Status at the end of study
	To specify the contents of analysis.
			
6.1.4.2.1. Datasets Analyzed
 
Delete the underlined part below:
 
For the above analysis items, the following analysis will be performed for merged treatment group.
	To correct the clerical error.

Ver.	Date	Author	Revised Content	Reason for Revision
			
6.2.1. Distribution of Demographics
 
Add the endpoints below:
 
Insomnia
 
 • Duration of disease (years) • Initial episode/recurrence • Non-pharmacological therapy 
Depression
 
 • Duration of disease (years) • Initial episode/recurrence • Psychotherapy 	To add the endpoints.
			
6.2.3. Medication History and Concomitant Medications
 
Add the endpoints below:
 
Analysis items:
 
Previous use of hypnotics [Yes (previous use of Benzodiazepine hypnotics, previous use of Non-benzodiazepine hypnotics, previous use of other hypnotics), No]
	To add the endpoints.

Ver.	Date	Author	Revised Content	Reason for Revision
			
7.1.1. Change from Baseline in Sleep Latency by Actigraphy
 
(1) Add the underlined part below: As the analyses for primary endpoints, summary statistics and two-sided 95% confidence interval (CI) of the mean will be calculated for both change and percentage change from baseline to the end of treatment period
 
(2) Add this section.
 
(3) Add the underlined parts below: For observed value at each time point, case plots will be displayed, and summary statistics and two-sided 95% CI of the mean will be calculated. Mean plots with +/- SD will be also displayed at each time point.
	
To add the endpoints and analysis methods.

Ver.	Date	Author	Revised Content	Reason for Revision
			
7.2.1. Secondary Endpoints and the Analytical Methods
 
(1) Add the underlined part below: As the analyses for primary endpoints, summary statistics and two-sided 95% confidence interval (CI) of the mean will be calculated for both change and percentage change from baseline to the end of treatment period
 
(2) Add this section.
 
(3) Add the underlined parts below: For observed value at each time point, case plots will be displayed, and summary statistics and two-sided 95% CI of the mean will be calculated. Mean plots with +/- SD will be also displayed at each time point.
	To add the endpoints and analysis methods.
			
7.3.2. Hamilton Rating Scale for Depression-17 (HAM-D17)
 
Modify the categories below:
 
(Before) HAM-D17 total score [0<=<8, 8<=<17, 17<=<23, 24<=]
 
(After) HAM-D17 total score [0<=<8, 8<=<17, 17<=<24, 24<=]
 
Add the endpoints below:
 
 • HAM-D17 total score (except for sleep related score) • HAM-D17 total score (sleep related score) 	To correct the clerical error and add the endpoints.

Ver.	Date	Author	Revised Content	Reason for Revision
			
7.3.3. 3 Dimensional Sleep Scale (3DSS)
 
(2) Add the underlined parts below: For phase scale score, quality scale score and quantity scale score, summary statistics will be calculated and case plots will be displayed.
 
(3) Add this section
	To add the endpoints.
			
7.3.4. Correlation between Endpoints
 
Add this whole section.
	To add the analysis.
			
8.1.2. Display of TEAE
 
7) Add this section.
	To add the analysis.
			
9. LISTING
 
Add this whole section.
	To add the analysis.
			
10.6. Examination of Subgroups
 
Add this whole section.
	To add the analysis.
